8.1.2 Reactogenicity (Solicited Local and Systemic Events)

Reactogenicity events are AEs that are common and known to occur following administration of this type of study vaccine. The subject will be instructed on noting the presence and severity of symptoms through D8 after administration of study vaccine: The following Toxicity Grading Scales will be used to grade solicited local (injection site) and systemic (subjective and quantitative) reactions:

Local (Injection Site) Reaction	Mild (Grade 1)	Moderate (Grade 2)	Severe (Grade 3)
Pain – experienced without touching the injection site (spontaneous discomfort)	No pain medication or it requires use of a non- narcotic pain reliever ≤24hours OR does not interfere with activity	Repeated use of non- narcotic pain reliever >24 hours OR interferes with activity	Any use of narcotic pain reliever OR prevents daily activity
Tenderness – hurts only when injection site is	Discomfort only to touch	Discomfort with movement	Significant discomfort at rest

Table 3: Local (Injection Site) Reactogenicity Grading

DMID/NIAID/NIH

Local (Injection Site) Reaction	Mild (Grade 1)	Moderate (Grade 2)	Severe (Grade 3)
touched or the arm is moved			
Pruritus (Itching)	Does not interfere with daily activity	Interferes with daily activity	Prevents daily activity
Ecchymosis (Bruising)*	Does not interfere with daily activity	Interferes with daily activity	Prevents daily activity
Induration (Hardness)/Swelling*	Does not interfere with daily activity	Interferes with daily activity	Prevents daily activity

* Will also be measured in mm but size will not be used as halting criteria.

Erythema (redness), ecchymosis, and induration (hardness)/swelling as analyzed by measurement will be graded as follows:

 Table 4: Local (Injection Site) Reactogenicity Measurements

Local (Injection Site) Reaction	Mild (Grade 1)	Moderate (Grade 2)	Severe (Grade 3)
Ecchymosis (Bruising)*	25mm – 50mm	51 mm – 100mm	>100 mm
Erythema (Redness)*	25 mm – 50 mm	51 mm – 100 mm	>100 mm
Induration (Hardness)/Swelling*	25 mm – 50 mm	51 mm – 100 mm OR interferes with activity	>100 mm OR prevents daily activity

*Will not be used as halting criteria.

Note: Ecchymosis and Induration/Swelling should be evaluated and graded using the symptom scale as well as the actual measurement.

Table 5: Subjective Systemic Reactogenicity Grading

Systemic (Subjective)	Mild (Grade 1)	Moderate (Grade 2)	Severe (Grade 3)

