8.6 Halting Rules

8.6.1 Study Halting Criteria

Further enrollment and study vaccinations will be halted for SMC review/recommendation if any of the following are reported:

- Any subject experiences ulceration, abscess, or necrosis at the injection site related to study vaccination.
- Two or more subjects who have received at least one dose of study vaccine to date experience the same (at MedDRA PT level) severe (grade 3) study vaccine-related unsolicited adverse event.
- Two or more subjects who have received at least one dose of study vaccine to date experience a severe (grade 3) study vaccine-related laboratory adverse event in the same laboratory parameter.
- Two or more subjects who have received at least one dose of study vaccine to date experience the same severe (grade 3) solicited injection site adverse event that persists for 3 or more days

DMID/NIAID/NIH

and does not resolve or decrease to a lower grade (The size [measured in mm] of ecchymosis, erythema and induration/swelling will not be used as a halting criterion).

- Two or more subjects who have received at least one dose of study vaccine to date experience the same severe (grade 3) study vaccine-related solicited systemic adverse event that persists for 3 or more days and does not resolve or decrease to a lower grade (Subjective systemic reaction corroborated by study personnel).
- Any subject experiences a study vaccine-related laryngospasm, bronchospasm, or anaphylaxis within 1 day of study vaccination.
- Any subject experiences a study vaccine-related allergic reaction (e.g., generalized urticaria) within 3 days of study vaccination.
- Any subject experiences a study vaccine-related SAE from the time of the first study vaccination through the subject's last study visit.

Grading scales for solicited local (injection site) and systemic (subjective and quantitative) reactions are included in Section 8.1.2.

If any of the halting rules above are met following any subject receipt of any vaccination, the study will not continue with the remaining enrollments or study vaccinations without a review by and recommendation from the SMC to proceed. DMID retains the authority to suspend additional enrollment and study interventions/ administration of study product during the entire study, as applicable.

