9.3.1. Solicited Events and Symptoms

Systemic solicited adverse events were collected pre-vaccination, and systemic and local solicited adverse events were collected 30 minutes post-vaccination and then daily for 7 days after each vaccination and graded on a scale of 0 (absent), 1 (mild), 2 (moderate) and 3 (severe). The grading scales are presented in Table 4 and Table 5. Systemic events include: arthralgia, fever, feverishness, fatigue, headache, malaise, myalgia, nausea, and vomiting. Local events include: ecchymosis severity and measurement, erythema measurement, induration/swelling severity and measurement, pain, pruritus, and tenderness.

The proportion of subjects reporting at least one solicited adverse event will be summarized for each solicited adverse event, any systemic symptom, any local symptom, and any symptoms. The 95% confidence interval (CI) calculated using Clopper-Pearson methodology from a binomial distribution (SAS Proc Freq with a binomial option) will be presented (Table 27).

For each systemic and local event, any systemic event, any local event, and any solicited event, the maximum severity over 7 days after each vaccination will be summarized for the Safety population. The number and percentage of subjects reporting each event will be summarized by the maximum severity and treatment group, separately for each vaccination and over all vaccinations. For each event the denominator is the number of subjects with non-missing data for the specific event (Table 28).

The number of subjects reporting a solicited adverse event will be summarized for each day post vaccination for each vaccination and for all vaccinations combined both in a summary table (Table 29, Table 30, Table 31, Table 32, Table 33, Table 34, Table 35, and Table 36) and graphically in a bar chart (Figure 11, Figure 12, Figure 13, Figure 14, Figure 15, Figure 16, Figure 17, and Figure 18). A comparison of the event rate for each treatment group between vaccination 1 and vaccination 3 will be presented (Table 37). The duration of solicited adverse events will be summarized by dose number and treatment group (Table 38).

Solicited adverse events by subject will be presented in Listing 8 and Listing 9.

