12.2.2 Displays of Adverse Events

Table 4: Solicited Adverse Event Grading Scale – Local (Injection Site) Reactogenicity Grading

Local (Injection Site) Reaction	Mild (Grade 1)	Moderate (Grade 2)	Severe (Grade 3)
Pain – experienced without touching the injection site (spontaneous discomfort)	No pain medication or it requires use of a non-narcotic pain reliever ≤24hours OR does not interfere with activity	Repeated use of non-narcotic pain reliever >24 hours OR interferes with activity	Any use of narcotic pain reliever OR prevents daily activity
Tenderness – hurts only when injection site is touched or the arm is moved	Discomfort only to touch	Discomfort with movement	Significant discomfort at rest
Pruritus (Itching)	Does not interfere with daily activity	Interferes with daily activity	Prevents daily activity
Ecchymosis (Bruising) Severity ^a	Does not interfere with daily activity	Interferes with daily activity	Prevents daily activity
Induration (Hardness)/Swelling Severity ^a	Does not interfere with daily activity	Interferes with daily activity	Prevents daily activity
Ecchymosis (Bruising) Measurement ^b	25mm – 50mm	51 mm – 100mm	>100 mm
Erythema (Redness) Measurement ^b	25 mm – 50 mm	51 mm – 100 mm	>100 mm
Induration (Hardness)/Swelling Measurement ^b	25 mm – 50 mm	51 mm – 100 mm OR interferes with activity	>100 mm OR prevents daily activity

^a Will also be measured in mm but size will not be used as halting criteria.

^b Will not be used as halting criteria.

Systemic	Mild (Grade 1)	Moderate (Grade 2)	Severe (Grade 3)
Feverishness (Chills/Shivering/Sweating)	No interference with daily activity	Some interference with daily activity	Significant interference, prevents daily activity
Fatigue (Tiredness)	No interference with daily activity	Some interference with daily activity	Significant interference, prevents daily activity
Malaise (General Unwell Feeling)	No interference with daily activity	Some interference with daily activity	Significant interference, prevents daily activity
Myalgia (Body Aches/Muscular Pain) ^a	No interference with daily activity	Some interference with daily activity	Significant interference, prevents daily activity
Arthralgia (Joint Pain) ^a	No interference with daily activity	Some interference with daily activity	Significant interference, prevents daily activity

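### The induration/swelling row of the measurement scale mixes size with function, so its Measurement row in the reactogenicity tables is not a size grade like the other two

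*Protocol*

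**What the plan says.** Protocol 8.1.2 grades induration/swelling on two scales. Table 3 grades it by effect on daily activity. Table 4 is introduced with the words "Erythema (redness), ecchymosis, and induration (hardness)/swelling as analyzed by measurement will be graded as follows". A note under Table 4 confirms that two scales are meant: "Ecchymosis and Induration/Swelling should be evaluated and graded using the symptom scale as well as the actual measurement".

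In Table 4 the ecchymosis and erythema rows use millimetre bands only: 25–50, 51–100 and over 100 mm. The induration/swelling row uses the same bands but adds a functional alternative at two grades. Grade 3 is ">100 mm OR prevents daily activity". SAP Table 4 labels this row as a measurement and keeps both clauses; its Grade 2 is "51 mm – 100 mm OR interferes with activity".

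SAP 9.3.1 lists "induration/swelling severity and measurement" among the local events. The shells for SAP Tables 27–36 and 38 give each its own row.

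On halting, the Table 3 footnote reads "Will also be measured in mm but size will not be used as halting criteria". Protocol 8.6.1 says "The size [measured in mm] of ecchymosis, erythema and induration/swelling will not be used as a halting criterion", and 8.6.2 has the same exclusion for individual subjects. The Table 4 footnote is not limited to size: it says only that the starred rows "will not be used as halting criteria". SAP Table 4 repeats that footnote for its Measurement rows.

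**The concern.** Solicited reactogenicity is a primary endpoint, and swelling is one of the two local reactions that protocol 2.3.1 reports as mainly raised over control in Phase III. A reader of the SAP tables will take the three Measurement rows as three size results on one scale. For induration/swelling that is not so: a small swelling that limits activity is shown as a Grade 2 or 3 measurement. The row then partly repeats the Severity row and cannot be compared with the ecchymosis and erythema rows.

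The planned displays do not let a reader undo this, because Listing 9 has a severity column but no column for millimetres.

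A secondary matter is the Table 4 footnote. It is unqualified and sits on a row that contains a functional clause, whereas the other halting text excludes size alone.

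**Working it through.** The plan states no figure on this point, so there is none to reproduce. The check enumerates what the grading rule does.

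**Inputs.** Functional grade f = 0–3 (protocol Table 3). Size grade s = 0–3 (mm bands of protocol Table 4; 0 means under 25 mm). Vaccine arm n = 20 (protocol 10.2).

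**Rule as written.** Measurement grade m = max(s, f) if f is 2 or 3, and m = s otherwise. Grade 1 has no functional clause.

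**All 4 × 4 = 16 combinations.** m differs from s in five:

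| Functional grade f | Size grade s | Measurement grade as written | From mm only |
|---|---|---|---|
| 2 | 0 | 2 | 0 |
| 2 | 1 | 2 | 1 |
| 3 | 0 | 3 | 0 |
| 3 | 1 | 3 | 1 |
| 3 | 2 | 3 | 2 |

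In the other 11, m = s. This is a count of cells, not a probability: the documents do not give the joint distribution of function and size.

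**Effect on the displays.**
- Incidence (Table 27): only the two cells with s = 0 turn a non-event into a Measurement event. One such vaccinee adds 1/20 = 5 percentage points. If there were no other event, the row would go from 0/20 (Clopper-Pearson 95% CI 0 to 1 − 0.025^(1/20) = 16.8%) to 1/20 (0.1% to 24.9%).
- Severity (Tables 28–36): all five cells shift the grade. Where s is 1 or 2 the subject is already counted, and only the severity category moves.
- Duration (Table 38): days with swelling under 25 mm but functional Grade 2 or 3 count as symptomatic days in the Measurement row.

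**Any Local Symptom.** The maximum over the two induration/swelling rows is max(f, m) as written and max(f, s) from mm only. These agree in all 16 cells, because m exceeds s only when m = f.

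**Halting.** Under 8.6.1 and 8.6.2, size does not count and functional Grade 3 counts through Table 3, subject to the 3-day persistence condition and, for the study rule, two subjects. Grade 3 on the Table 4 row covers 7 cells: 4 with f = 3, which can count, and 3 reached by size alone (f = 0, 1 or 2 with s = 3), which cannot. Removing the functional clauses from the row changes the halting result in 0 of 16 cells.

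**The case against.** The strongest reply is that little turns on this. The trial is descriptive and tests no hypothesis, the placebo group is not meant for comparison, and the Severity row next to it shows function cleanly. That stands as a limit on the consequence. It does not make a row labelled as measurement correct.

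It can also be said that the documents do not show how the database derives the grade, and that the note under Table 4 points to the actual measurement. That is fair: the effect described is the rule as written, not demonstrated practice. It is also a reason to state the derivation in the SAP.

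Three stronger readings are tempting and are not supported:
- A reader might infer that the row does not report size. It does in part: Grade 1 is size only, Grades 2 and 3 keep their mm bands, and the grade equals the size grade in 11 of 16 cells.
- A reader might infer that a Grade 3 swelling that prevents activity both counts and does not count for halting. The halting sections and the Table 3 footnote exclude only size, so such an event counts through Table 3. The Table 4 footnote can be read consistently with this, as saying that the measurement scale is not the halting scale.
- A reader might apply the swelling rates in protocol 2.3.1 to size the problem: 0.023 × 20 = 0.46 and 0.043 × 20 = 0.86 vaccinees. Those rates are for swelling not restricted to Grades 2–3, the higher one comes from a 20 µg Phase II group, and the protocol says most Phase III events were Grade 1. They do not estimate the number of affected grades.

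**Conclusion.** The reporting fault holds. The induration/swelling Measurement row is a composite of size and function, in a display of a primary safety endpoint. As written, function sets the grade in 5 of 16 combinations, and in two of them a swelling below the smallest size band becomes a Measurement event worth 5 percentage points per vaccinee. How many subjects this will affect cannot be estimated from the documents, and the number may be zero.

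The conclusion assumes that the grade is assigned literally from the table. It does not extend to Any Local Symptom or to any halting outcome under 8.6.1 and 8.6.2. On halting, what remains is an over-broad footnote to clarify, not two opposing rules.

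**What to change.** In the SAP, state that the induration/swelling grade in the Measurement rows of Tables 27–36 and 38 is derived from millimetres only, as for ecchymosis and erythema, and that the functional grade is reported in the Severity row. Align protocol Table 4 and SAP Table 4 with this. If the protocol is not to be amended, the SAP can make the change alone and record the departure from protocol Table 4.

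Separately, the sponsor should reconcile the Table 4 footnote, and its copy in SAP Table 4, with the Table 3 footnote, 8.6.1 and 8.6.2, so that a single statement says what lies outside the halting rules. Which rule applies is for the sponsor to decide.

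The cost is a wording change to one table row and one footnote in each document. No new assessment is needed, since protocol 8.1.2 already requires both the size in millimetres and the functional grade. The small downside is fewer Grade 2–3 entries in the Measurement row.

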8.1.3 Unsolicited Adverse Events

8.1.4 Serious Adverse Events (SAEs)

An AE or suspected adverse reaction is considered a serious adverse event (SAE) if, in the view of either the site principal investigator or sponsor, it results in any of the following outcomes:

- o Death,
- \circ a life-threatening adverse event¹,
- o inpatient hospitalization or prolongation of existing hospitalization,

- a persistent or significant incapacity or substantial disruption of the ability to conduct normal life functions, or
- a congenital anomaly/birth defect.
- Important medical events that may not result in death, be life-threatening, or require hospitalizations may be considered serious when, based upon appropriate medical judgment they may jeopardize the patient or subject and may require medical or surgical intervention to prevent one of the outcomes listed in this definition. Examples of such medical events include allergic bronchospasm requiring intensive treatment in an emergency room or at home, blood dyscrasias or convulsions that do not result in inpatient hospitalization, or the development of drug dependency or drug abuse.

¹Life-threatening adverse event. An AE is considered "life-threatening" if, in the view of either the site principal investigator or sponsor, its occurrence places the patient or subject at immediate risk of death. It does not include an AE that, had it occurred in a more severe form, might have caused death.

SAEs will be:

- Assessed for severity and relationship to study product and alternate etiology (if not related to study product) by a licensed study physician listed on the Form FDA 1572 or by the Institution as the site Principal Investigator or Sub-Investigator.
- Recorded on the appropriate SAE data collection form and eCRF.
- Followed through resolution by a licensed study physician (for IND studies, a physician listed on the Form FDA 1572 as the site Principal Investigator or Sub-Investigator).
- Reviewed and evaluated by DMID, an Independent Safety Monitor (ISM), the SMC (periodic review unless related), and the IRB/IEC.

8.2 Specification of Safety Parameters

Safety will be assessed by the frequency and severity of:

- 1. Serious adverse events (see Section 8.1.4) occurring from the time of the first study vaccination through the last study visit (Day 360).
- 2. Solicited Adverse Events (see Section 8.1.2) reactogenicity events occurring on the day of each study vaccination through Day 8 after each study vaccination:

DMID/NIAID/NIH

a) Injection site reactions including pruritus (itching), ecchymosis (bruising), erythema (redness), induration (hardness)/swelling, pain, and tenderness.

b) Systemic reactions including fever, feverishness (chills/shivering/sweating), fatigue (tiredness), malaise (general unwell feeling), myalgia (body aches/muscular pain exclusive of the injection site), arthralgia (joint pain exclusive of the injection site), headache, nausea, and vomiting.

- 3. Clinical safety laboratory AEs (see **Appendix B**) at Day 8 after each study vaccination. Parameters to be evaluated include WBC, ANC, AEC, Hgb, PLT, Cr, and ALT (Section 2.3.1).
- 4. Unsolicited Adverse Events (see Section 8.1.3) non-serious adverse events occurring from the time of the first study vaccination until Day 57 then from Day 180 through Day 208. Unsolicited AEs will be collected at all visits from the time of the first study vaccination until D57, then from Day 180 through 208. Any safety-related changes that occur post-vaccination during these timeframes and that represent an increase in grade must be recorded on the eCRF. Thereafter, recording will be limited to SAEs.

All Grade 1, 2, and 3 changes except for Grade 1 and 2 solicited adverse events must be assessed for relatedness to the study vaccination. The assessment of causality must be determined by a study clinician licensed to make medical diagnoses and listed on the FDA Form 1572 as the site principal investigator or sub-investigator.

8.3 **Reporting Procedures**

Solicited injection site and systemic reactogenicity events will be documented and reported from the time of each study vaccination through D8 after each study vaccination.

Unsolicited non-serious AEs will be documented and reported at all visits from signing of the ICF onwards until D57, then from Day 180 through Day 208.

SAEs will be collected from the time of the first study vaccination through the last study visit (Day 360).

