Subjects will be observed for 30 minutes after vaccination. The occurrence of solicited injection site and systemic reactogenicity events will be measured from the time of study vaccination through Day 8 after each vaccination. These will be ascertained through use of an electronic Memory (e-Memory) aid, a telephone call on Day 4 after each dose of vaccine, a Day 8 clinic visit, and potentially at the Day 15 clinic visit after each dose of vaccine. Unsolicited AEs will be collected from vaccination through D29 after each vaccination. SAEs will be collected from the time of the first study vaccination through the last study visit (Day 360).

The study includes multiple phlebotomy time points for immunogenicity and blood collection for future use at Visit 1 and Days 8, 15, and 29 after each vaccination. The durability of the immune response and future use collection will be assessed at 5 months after the first boost (Day 180) and at 6 months after the second boost (Day 360).

Note: The study day and the day after boost vaccination may not always align due to the study windows (See Appendix A) for the appropriate windows of time for each study visit.

Schematic of Study Design: See Figure 1.

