8.4 Type and Duration of Follow-up of Subjects after Adverse Events

Solicited AEs are reactogenicity events occurring on the day of each study vaccination through Day 8 after each study vaccination. Unsolicited AEs are non-serious adverse events occurring from the time of the first study vaccination until Day 57, then from Day 180 through Day 208. AEs will be assessed, and followed from initial recognition of the AE through end of the protocol defined follow-up period. AEs will be followed to adequate resolution. Resolution of an AE/SAE is defined as the return to pretreatment status or stabilization of the condition with the expectation that it will remain chronic.

DMID/NIAID/NIH

SAEs will be collected from the time of the first study vaccination through the last study visit (Day 360). SAEs will be followed to adequate resolution or stabilization even if this extends beyond the study-reporting period.

Follow-up procedures, evaluations, and outcomes will be recorded on the appropriate eCRF.

8.5 Procedures to be Followed in the Event of Abnormal Laboratory Test Values or Abnormal Clinical Findings

Samples will be collected for hematology, serum chemistry and urinalysis. The study clinician licensed to make medical diagnoses and listed on the Form FDA 1572 as the site principal investigator or sub-investigator must review the laboratory results, document this review, and record attribution to study product and clinical significance for all abnormal laboratory values on the Local Laboratory eCRF. Abnormal laboratory results meeting the protocol-defined toxicity grading scale are considered adverse events; however, they ARE NOT reported as unsolicited AEs on the Adverse Event eCRF. The laboratory reports must be filed with the source documents.

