- m) Solicited AEs: Inclusive of solicited injection site reactions and systemic reactogenicity events performed on the day of each study vaccination through at least D8 after each study vaccination (see Sections 8.1.2). Unsolicited AEs: Collection of unsolicited AEs from time of first vaccination through D57; then from Day 180 208. SAEs: SAEs will be collected from the time of the first study vaccination through the last study visit (Day 360).
- n) Volumes are the maximum volumes expected to be drawn. Samples may be fasted or non-fasted. The total volume at an unscheduled or early termination visit will not exceed the individual time point volume.
- $\{\ \}$ If indicated based upon timing and/or symptoms.
- * See Section 7.1.1 regarding details of medical history to be collected.
- ** Telephone Visit

DMID/NIAID/NIH

107

CONFIDENTIAL

Version 2.0

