9.3. Adverse Events

When calculating the incidence of adverse events (i.e., on a per subject basis), each subject will only be counted once and any repetitions of adverse events within a subject will be ignored; the denominator will be the total number of subjects in the safety population or the number of subjects in the safety population who received a given dose, first dose, second dose, or third dose as appropriate. All adverse events reported will be included in the summaries and analyses.

An overall summary of adverse events is presented in Table 25.

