14.3.1 Displays of Adverse Events

Overall Summary of Adverse Events Table 25:

	HEV (N =	/-239 = xx)	Plac (N =	cebo = xx)	All Subjects (N = xx)				
Subjects ^a with	n	%	n	%	n	%			
At least one local solicited adverse event	x	x	x	x	x	x			
At least one systemic solicited adverse event	x	x	x	x	x	x			
At least one unsolicited adverse event	x	x	х	x	x	х			
At least one related unsolicited adverse event	x	x	х	x	x	x			
Mild (Grade 1)	x	x	x	x	x	x			
Moderate (Grade 2)	х	х	x	х	х	x			
Severe (Grade 3)	x	x	x	x	x	x			
At least one severe (Grade 3) unsolicited adverse event	x	x	x	x	x	x			
Related	х	х	x	х	х	х			
Not related	x	x	x	x	x	x			
At least one clinical safety laboratory adverse event	x	x	x	x	x	x			
At least one serious adverse event ^b	x	x	x	x	x	x			
At least one related, serious adverse event	x	x	x	x	x	x			
At least one adverse event leading to early termination ^c	х	x	x	x	x	x			

N = Number of subjects in the Safety Population

^a Subjects are counted once for each category regardless of the number of events.
 ^b A listing of Serious Adverse Events is included in Table 43.

^c As reported on the Adverse Event eCRF.

Table 26:Adverse Events Occurring in 5% of Subjects in Any Treatment Group by MedDRA
System Organ Class and Preferred Term, and Treatment Group - Safety Population

Preferred Term	MedDRA System Organ Class		HEV-239 (N=X))		Placebo (N=X)		All Subjects (N=X)			
		n	%	Events	n	% Events		n	%	Events	
Serious Adverse Events											
All	All	х	х	х	х	х	х	х	х	х	
PT1	SOC1	х	х	х	х	х	х	х	х	х	
Etc.	Etc.										
Other (Non-serious) Adverse	e Events										
All	All	х	х	х	х	х	х	х	х	х	
PT1	SOC1	х	х	х	х	х	х	х	х	х	
Etc	Etc										

N = number of subjects in the Safety Population (number of subjects at risk).

n= number of subjects reporting event.

Events= total frequency of events reported.

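### Protocol 8.3 starts unsolicited AE documentation at consent while every other section starts at vaccination, and the shells of SAP Tables 25, 26 and 41 have no onset rule to keep pre-dose events out (minor)

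*Protocol*

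**What the plan says.** The start of the unsolicited AE window is given in six places, and one of them differs.

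| Place | Start |
|---|---|
| Protocol 8.3 | "from signing of the ICF onwards until D57" |
| Protocol 8.2, item 4 | "Unsolicited AEs will be collected at all visits from the time of the first study vaccination until D57" |
| Protocol 8.4 | "Unsolicited AEs are non-serious adverse events occurring from the time of the first study vaccination until Day 57" |
| Protocol 3.1 | "Unsolicited AEs will be collected from vaccination through D29 after each vaccination" |
| Protocol Appendix A, note m | "Collection of unsolicited AEs from time of first vaccination through D57" |
| SAP 4.5.1, item 4 (and SAP Table 1, note m) | first vaccination |

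On the analysis side, SAP 9.3 states: "All adverse events reported will be included in the summaries and analyses". The SAP has no treatment-emergent definition and no filter on onset date.

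The shells differ in how they handle time. Tables 39-40 and 42-43 are divided into post-dose periods that begin at Day 1. Table 25 (for example the row "At least one unsolicited adverse event"), Table 26 and Table 41 show no period at all.

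**The concern.** Section 8.3 is the Reporting Procedures section, so site staff may well follow it when entering events. If they do, the database will hold events with onset after consent and before any study product. Such events say nothing about the vaccine, yet no sentence in the SAP expressly removes them from the tables that lack a time window.

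The stake is the descriptive, all-causality safety picture. Protocol 10.2 says the five placebo subjects are not meant as a comparison group, so the rate among the 20 vaccinees will be read on its own, and extra events would raise it directly. A second cost is internal disagreement: Table 41 and the any-time column of Tables 39-40 could give different totals for what a reader would take to be the same events.

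**Working it through.** **1. The plan's own figure.** The only AE-incidence calculation in the documents is the table in Protocol 10.2, the probability of seeing at least one event among 20. The formula 1 - (1 - p)^20 at p = 0.01%, 0.1%, 1%, 10% and 20% gives 0.20%, 1.98%, 18.21%, 87.84% and 98.85%, exactly as printed. It is not in dispute. The same formula is used in step 5.

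**2. Following one event through the rules.** Take a mild illness that begins after the screening visit and before Day 1.

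- Is it recorded? Yes under Protocol 8.3; no under 3.1, 8.2, 8.4 and Appendix A.
- Does the baseline rule remove it? No. Protocol 8.1.1 and SAP 4.5.1 treat only conditions already present at screening as baseline.
- Is it counted? Yes under SAP 9.3 read literally; no under the definition in SAP 4.5.1, item 4.
- Do the shells screen it out? Those of Tables 39-40 and 42-43 do. Those of Tables 25, 26 and 41 do not.

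The outcome depends on which of two conflicting sentences is followed, first at the site and then in programming.

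**3. Collection time.** Consent is signed at the start of screening (Protocol 6.1), and screening falls within 28 days before Day 1 (5.1). Post-dose collection is Days 1-57 plus Days 180-208: 57 + 29 = 86 days. The pre-dose share is d/(d + 86).

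| Consent to Day 1 | Share of collection time |
|---|---|
| 7 days | 7/93 = 7.5% |
| 14 days | 14/100 = 14.0% |
| 28 days | 28/114 = 24.6% |

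Twenty-eight days is the scheduled window. Protocol 6.2 provides for repeat laboratories if vaccination slips past it, so an individual subject could run longer.

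**4. What one event does.** With 20 vaccinees, one pre-dose event moves a preferred term from 0/20 (exact 95% CI 0 to 16.8%) to 1/20 = 5% (0.1 to 24.9%), the level named for Table 26. In the placebo arm, 1/5 = 20% (0.5 to 71.6%). At these arm sizes a single event in either arm reaches the Table 26 level.

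**5. How often.** The documents give no background rate, so r, the proportion of subjects with a new AE per 28 days, is an assumption shown as a range. With a constant rate, full 28-day screening and equal capture throughout, incidence over T days is 1 - (1 - r)^(T/28), and the chance of at least one pre-dose case among 20 is 1 - (1 - r)^20.

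| r | Expected vaccinees with a pre-dose AE (20r) | Chance of at least one | Any-AE proportion, 86 days | Same, 114 days |
|---|---|---|---|---|
| 2.5% | 0.5 | 40% | 7.5% | 9.8% |
| 5% | 1.0 | 64% | 14.6% | 18.8% |
| 10% | 2.0 | 88% | 27.6% | 34.9% |
| 20% | 4.0 | 99% | 49.6% | 59.7% |

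These are upper-end values. With 7 days from consent to Day 1 and r = 5%, the chance of at least one falls to 23%.

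**The case against.** The best reply is that the SAP has already settled the matter. SAP 4.5.1 defines unsolicited AEs from first vaccination, the relevant rows of Table 25 and the title of Table 41 use that term, and SAP 9.3.2 places Table 26 among the unsolicited summaries, presented by vaccination. The all-reported sentence in 9.3 sits beside rules on counting and denominators and need not override a definition. Both documents also describe an AE as tied in time to use of the product.

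Collection points the same way. The AE row of the schedule is blank at screening, Protocol 6.1 lists no AE review, and on Day 1 AE collection appears only after the injection. Before it, staff review interval changes in medical history. Exclusion for acute illness within 3 days of dosing thins pre-dose events further. Listing 10 and Table 45 show days post dose, so a stray event should be visible.

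Most of this stands, and it is why the point is minor. It does not close the gap. The SAP never says which sentence prevails, Table 26 is titled only as adverse events, and the shells of Tables 26 and 41 omit the split by vaccination that 9.3.2 describes.

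Three stronger inferences are tempting, and the documents support none of them:

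- *That about a quarter of reported AEs would predate Dose 1.* The 24.6% is a share of collection time. It becomes a share of events only with full-length screening, a constant rate and equal capture, and no AE assessment is scheduled in that period. Tables 25 and 41 also count subjects, not events.
- *That the vaccine arm is specifically disadvantaged.* Randomization is on Day 1, so earlier events fall on both arms alike.
- *That the primary safety result is compromised.* The primary unsolicited endpoint counts related events after vaccination, and an event before any product cannot be related. The related rows of Table 25 and Tables 42-43 are untouched for the same reason, and SAEs start at first vaccination in both 8.2 and 8.3.

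**Conclusion.** The inconsistency is real. Followed as written, Protocol 8.3 and SAP 9.3 could put pre-dose events into the all-causality unsolicited rows of Table 25 and into Tables 26 and 41, in either arm, and out of line with Tables 39-40. The effect is limited to descriptive tables.

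Within the scheduled screening window, the ceiling is just under a quarter of collection time, on the assumptions in steps 3 and 5. The actual effect is probably much less and could be nil if sites follow the visit schedule. Severity is minor. It is worth correcting because at 20 subjects one misplaced event is 5 percentage points, and the correction costs almost nothing.

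**What to change.** - **Protocol 8.3:** replace the consent start with first study vaccination, to agree with 3.1, 8.2, 8.4 and Appendix A. If recording from consent is intended, say so and keep those events apart.
- **SAP 9.3:** add one sentence. The AE summaries in Tables 25, 26 and 41 count only events with onset, or worsening in grade, after the first vaccination; any earlier event appears in a separate listing.

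The cost is one protocol phrase and one SAP sentence. Sample size, endpoints and visit procedures do not change.
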